6.4 Summary of Methods of Data Collection

An IVRS/IWRS will be used to screen, randomize, and manage study medication inventory. Data will be collected using eCRFs via a validated electronic data capture system (EDC). Source documents will be used and stored at the sites, and may include a patient's medical records, hospital charts, clinical charts, patient chart, copy of the EDC file, as well as the results of diagnostic tests such as laboratory tests, ultrasounds, x-rays, and ECGs. The videotapes captured for the Edinburgh Visual Gait assessment will be shipped or electronically transferred to Allergan and stored into an Image Repository. For patients \geq 6 years of age at day 1, the C-SSRS will be collected as a clinical interview and the scores will be collected from the designated site staff using an electronic data collection method (eg, electronic tablet).

A central laboratory will be used for the analysis of all blood samples. Blood samples for immunogenicity tests will be shipped by the central laboratory, analyzed by a specialty laboratory using validated assays, and the data will be transferred to Allergan.

7. Statistical Procedures

The database will be locked when all patients have completed the study. A detailed analysis plan will be generated prior to the final database lock. All planned analyses will be performed after the database has been locked and randomization data released.

7.1 Analysis Populations

Safety data will be analyzed on the basis of all treated patients based on the treatment received, defined as the safety population. Efficacy data, demographics, and background information will be analyzed on the basis of the modified intent-to-treat (mITT) population, defined as all randomized patients with a valid baseline MAS-B ankle score with knee extended and at least one post-baseline measurement at weeks 2, 4, or 6 for the MAS-B ankle score with knee extended and the CGI by Physician.

7.2 Collection and Derivation of Primary and Secondary Efficacy Assessments

At each scheduled office visit at weeks 2, 4, 6, 8, and 12, the patient's spasticity of the ankle will be evaluated using the MAS-B. MAS-B scores of 0, 1, 1+, 2, 3, or 4 will be coded as grades of 0, 1, 2, 3, 4, or 5, respectively. The MAS-B grade change from baseline to each post-randomization office visit and the primary endpoint, average change at weeks 4 and 6 using observed cases without imputation of missing values, will be derived for each patient. Additionally, a responder status will be determined according to whether or not a patient has at least a 1 grade reduction from baseline on the MAS-B.

The secondary efficacy measure CGI by Physician (for US FDA, CGI by Physician is a co-primary measure) will be measured at weeks 2, 4, 6, 8, and 12. CGI is a 9-point scale from -4 (very marked worsening) to +4 (very marked improvement). Each assessment is evaluated relative to the patient's baseline status obtained at day 1. The average of scores at weeks 4 and 6 using observed cases without imputation of missing values will be derived for CGI by Physician. Additionally, a responder status will be determined according to whether or not a patient has at least +1 score of CGI by Physician.

The secondary efficacy measures of MTS and GAS will also be collected at scheduled office visits according to the Schedule of Visits and Procedures in Table 1. The difference between slow (R2) and fast (R1) range of motion (R2 - R1; see Attachment 12.1.11 for a detailed description of the MTS) and respective change from baseline to each posttreatment office visit on the MTS will be derived. Multiple imputation (MI) method is only intended for MAS-B ankle score and the CGI by Physician as a sensitivity analysis. Missing values for other variables will not be imputed.

7.2.1 Primary Efficacy Variables

The primary efficacy variable is the grade change of MAS-B of the ankle plantar flexors with knee extended. The primary efficacy endpoint will be the average grade change from baseline in MAS-B at weeks 4 and 6. For US FDA only, the co-primary efficacy variables are the average grade change of MAS-B of the ankle plantar flexors with knee extended and the CGI by Physician. The co-primary efficacy endpoints will be the average grade change from baseline in MAS-B and the average CGI by Physician at weeks 4 and 6.

7.2.2 Secondary Efficacy Variables

CGI by Physician (for non-US FDA analyses) will be evaluated at weeks 2, 4, 6, 8, and 12. In addition to each timepoint, the average of the weeks 4 and 6 CGI by Physician will be analyzed. Functional goals, active and passive, using GAS by Physician will be evaluated separately relative to baseline at weeks 8 and 12. Secondary efficacy variables of MTS include the difference between slow (R2) and fast (R1) range of motion (R2 - R1) as well as respective change from baseline on the MTS for the ankle plantar flexors (with knee extended and knee flexed) at weeks 2, 4, 6, 8, and 12. Additionally changes from baseline for each R1 and R2 at each assessment point will be evaluated.

7.3 Hypothesis and Methods of Analysis

7.3.1 Primary Efficacy Analyses

The primary efficacy analyses will be based on the mITT population. The primary analysis will be conducted for the average change from baseline in MAS-B score at weeks 4 and 6. The statistical null hypothesis is that both higher dose (8 U/kg) and lower dose (4 U/kg) have the same mean as placebo. The alternative hypothesis is that at least one study dose has a different mean than placebo. The hypothesis will be tested based on the Least Square (LS) mean differences from an analysis of Mixed Model Repeated Measures (MMRM) at

significance level of 0.05. The primary variable will be summarized by treatment group. The difference of LS means of each dose group and the placebo group from MMRM model will be used to test the null hypothesis. The analysis will include observed data at weeks 2, 4, 6, 8, 12. The model will include baseline MAS-B as a covariate and factors of age group, treatment group, visit, treatment-by-visit interaction, study center, and previous botulinum toxin exposure. Age group is represented by stratification categories (≤ 6 years and > 6 years for age group). Baseline MAS-B grade is a continuous variable included as a covariate. Unstructured covariance structure will be used. Two tests will be performed based on the pairwise comparisons: 8 U/kg versus placebo and 4 U/kg versus placebo, each at a 0.05 significance level.

To control the type I error rate for the endpoint of the average change from baseline in MAS-B score at weeks 4 and 6, a gatekeeping approach will be used for this variable (Dmitrienko et al, 2005). Specifically, for average change from baseline in MAS-B, the LS mean difference of 8 U/kg versus placebo from the MMRM will be tested first. If the test is not statistically significant at the level of 0.05, the test of the LS mean of difference of 4 U/kg versus placebo will not be considered statistically significant regardless of its p-value. Otherwise, if the test for 8 U/kg is statistically significant, then the test for 4 U/kg versus placebo will be evaluated based on its p-value.

For sensitivity analysis purposes to supplement the primary analyses, an analysis of covariance (ANCOVA) model using MI for missing values will be conducted. A summary of the percentage of missing MAS-B scores by visit will also be provided. The ANCOVA will include baseline MAS-B score as a covariate and factors of age group, treatment group, study center and previous botulinum toxin exposure. Additional sensitivity analyses for the MAS-B changes from baseline at each assessment timepoint will also be performed using ANCOVA with the same model as specified above with observed data, and linear contrasts will be used to estimate the treatment differences between each study dose and placebo. In addition, the frequency distribution of the grade changes from baseline in the MAS-B, as well as the percentage of responders (with at least a 1 grade reduction in MAS-B), will be summarized by treatment group at each posttreatment office visit. A logistic regression analysis will also be performed on the responder status at each posttreatment visit with a covariate of baseline MAS-B and factors of age group, treatment group, study center, and previous botulinum toxin exposure, if applicable. The additional analyses will be conducted using observed cases unless stated otherwise.

For US FDA only, CGI by Physician will be a co-primary variable (see Section 7.7 for description of analyses).

7.3.2 Secondary Efficacy Analyses

The observed cases will be used for secondary efficacy analyses unless stated otherwise. CGI by Physician will be rated at study weeks 2, 4, 6, 8 and 12. CGI by Physician will be summarized and analyzed by MMRM as the average of values at weeks 4 and 6 as well as ANCOVA at each assessment timepoint using observed cases. The frequency distribution of the CGI scores, as well as the percentage of responders (CGI score of at least +1), will be summarized by treatment group at each posttreatment timepoint. A logistic regression analysis will also be performed on the responder status at each posttreatment timepoint with factors age group, treatment group, study center, and previous botulinum toxin exposure, if applicable. For GAS by Physician, scores for each of the 2 goals at weeks 8 and 12 will be summarized by treatment group and analyzed by ANCOVA as specified in Section 7.3.1 to assess the treatment differences. For MTS of the ankle of the study lower limb with knee extended and knee flexed, the difference between slow and fast motion (R2 - R1) and the individual R2 and R1 values in degree, as well as the respective changes from baseline, will be summarized by treatment group and analyzed by ANCOVA.

7.3.4 Safety Analyses

Safety variables, including the incidence of adverse events, the incidence of suicide-related events using the C-SSRS (for patients \geq 6 years of age at day 1), laboratory test values and changes from baseline, as well as vital signs and their change from baseline, will be summarized by treatment group using the safety population. The Medical Dictionary for Regulatory Activities (MedDRA) nomenclature will be used to code adverse events and medical history. The incidence of adverse events (both pretreatment events and treatment-emergent events) will be tabulated by primary system organ class and preferred term for each treatment group. Possible distant spread of toxin adverse events will be assessed using a standardized methodology.

Descriptive statistics will be presented for vital signs and numeric laboratory tests and the respective changes from baseline. All laboratory values will be presented by descriptive statistics. In addition, laboratory values outside the normal reference ranges for each patient at each applicable visit will be identified and evaluated against baseline via shift table analysis. Potentially clinically significant abnormal values may be identified or summarized descriptively.

Immunogenicity results for each patient will be reported as positive, negative, or inconclusive. Correlations between immunogenicity results and other variables may be performed if warranted.

Approval Date: 25-Jul-2016

7.4 Subgroup Analyses

Among the efficacy variables, the primary and selected secondary efficacy variables will be summarized by baseline MAS-B score (2 and > 2), age (\leq 6 years and $>$ 6 years) and previous exposure to botulinum toxin.

7.5 Sample Size Calculation

Approximately 412 patients will be enrolled to ensure that at least 351 patients (117 per treatment group) will complete the study.

Using a 2-sample t-test, a significance level of 0.05, and the assumptions in Table 4, the power for MAS-B change from baseline is 94% (PASS, Hintze, 2008). The calculation is based on assumptions for 8 U/kg group and placebo group. Since there are 2 co-primary endpoints for the US FDA analysis, for 8 U/kg group the power for CGI by Physician is calculated to be 97%, and the overall power for the US FDA co-primary endpoints will be at least 91%. The assumptions for MAS-B were based on results of completed Studies BTX108509 and BTX108512; the estimates for CGI were based on results of completed Study 191622-021.

Table 4 **Sample Size Assumptions and Power Calculations**

Endpoint	Average of Week 4 and 6 for 8 U/kg group	Average of Week 4 and 6 for Placebo group	Standard Deviation	Power
MAS-B Change from Baseline	-0.8	-0.45	0.75	94%
CGI by Physician (Co-primary for US FDA Analysis)	1.2	0.6	1.2	97%
Overall Endpoints				91%

CGI = Clinical Global Impression of Overall Change; MAS-B = Modified Ashworth Scale – Bohannon; US FDA = United States Food and Drug Administration

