Safety data will be analyzed on the basis of all treated patients based on treatment received, defined as the safety population. Efficacy data will be analyzed on the basis of the modified intent-to-treat (mITT) population, defined as all randomized patients with a valid baseline MAS-B ankle score with knee extended and at least one post-baseline measurement at weeks 2, 4, or 6 for the MAS-B ankle score with knee extended and the CGI by Physician. The primary efficacy endpoint will be the average grade change from baseline in the MAS-B ankle score at weeks 4 and 6. For US FDA only, the average grade change from baseline in MAS-B ankle score at weeks 4 and 6 and the average CGI by Physician at weeks 4 and 6 will be analyzed as co-primary endpoints. Mixed Model Repeated Measures (MMRM) with unstructured covariance structure will be performed with baseline MAS-B as a covariate and factors of age group, treatment group, visit, treatment-by-visit interaction, study center, and previous botulinum toxin exposure. Continuous secondary and other efficacy variables will be summarized by treatment group and analyzed by Analysis of Covariance (ANCOVA). Categorical efficacy

[figure not shown]
BOTOX® (Botulinum Toxin Type A) Purified Neurotoxin Complex

variables, such as the responder status for MAS-B, will be analyzed by logistic regression. All statistical tests will be 2-sided with a significance level of 0.05. Safety variables, such as the adverse event incidence rate, vital signs and changes from baseline in vital signs, the incidence of suicide-related events, and laboratory test values and their changes from baseline, will be summarized by treatment group.

Sample Size Calculation:

Approximately 412 patients will be enrolled to ensure that at least 351 patients (117 per treatment group) will complete the study. Using a 2-sample t-test, a significance level of 0.05, and the assumptions in the table below, the power for MAS-B change from baseline is 94% (PASS, [Hintze, 2008](#)). The calculation is based on assumptions for 8 U/kg group and placebo group. Since there are 2 co-primary endpoints for the US FDA analysis, for 8 U/kg group the power for CGI by Physician is calculated to be 97%, and the overall power for the US FDA co-primary endpoints will be at least 91%. The assumption for MAS-B were based on results of completed Studies BTX108509 and BTX108512; the estimates for CGI were based on results of completed Study 191622-021.

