5.4 Treatment Allocation Ratio and Stratification

A centralized randomization scheme stratified by age and baseline MAS-B ankle score will be prepared by Allergan. Patients will be randomized to 1 of 3 treatment groups in a 1:1:1 ratio within each combination of strata. Randomization will be dispensed by the IVRS/IWRS. The stratification categories are as follows:

- Age (≤ 6 years and > 6 years)
- Baseline (day 1) MAS-B score of the ankle with knee extended (MAS-B = 2 and MAS-B > 2)

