7.7.1 Primary Efficacy Analyses

There are 2 co-primary endpoints: the average grade change from baseline in the MAS-B ankle score at weeks 4 and 6 and the CGI by Physician at weeks 4 and 6. For both the co-primary endpoints, the statistical null hypothesis is that both the higher dose (8 U/kg) and the lower dose (4 U/kg) have the same mean as placebo. The alternative hypothesis is that at least one study dose has a different mean than placebo.

In addition to the primary statistical analyses cited in Section 7.3.1 for the average of the observed grade change from baseline in MAS-B, the average observed CGI by Physician at weeks 4 and 6 will also be analyzed using the same statistical method (with the same MMRM model).

The Hochberg procedure ([Hochberg and Tamhane, 1987](#)) will be used to control the family-wise type I error rate. With 2 doses and 2 co-primary endpoints in each dose, the maximum p value for the 2 co-primary endpoints in each dose will be used in the Hochberg procedure. We first define the following values:

- p11: p value for Botox 8 U/kg vs placebo comparing MAS-B
- p12: p value for Botox 4 U/kg vs placebo comparing MAS-B
- p21: p value for Botox 8 U/kg vs placebo comparing CGI
- p22: p value for Botox 4 U/kg vs placebo comparing CGI
- p1 = max(p11, p21), p2 = max(p12, p22).

p1 and p2 will be sorted in an increasing order to get $p(1) \leq p(2)$. The following decision rule will then be applied:

Step 1: If $p(2) \leq 0.05$, both doses are considered efficacious; otherwise go to step 2.

Step 2: If $p(1) \leq 0.025$, its corresponding dose is considered efficacious; otherwise go to step 3.

Step 3: Neither dose is considered efficacious.

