### 10.1               **Primary Efficacy Analyses**

There are 2 co-primary endpoints: the average grade change from baseline in the MAS-B ankle score with knee extended at weeks 4 and 6 and the average CGI by Physician at weeks 4 and 6. For both co-primary endpoints, the statistical null hypothesis is that both the higher dose (8 U/kg) and the lower dose (4 U/kg) have the same mean as placebo. The alternative hypothesis is that at least one study dose has a different mean than placebo. In addition to the primary statistical analyses cited in Section 5.2.1 for the average grade change from baseline in MAS-B ankle score with knee extended at weeks 4 and 6, the average CGI by Physician at weeks 4 and 6 will be analyzed using the same statistical method with a same MMRM model in Section 5.3.1.

The Hochberg procedure (Hochberg and Tamhane, 1987) will be used to control the family-wise type I error rate. With 2 doses and 2 co-primary endpoints in each dose, the maximum p-value for the 2 co-primary endpoints in each dose will be used in the Hochberg procedure. We first define the following values:

p11: p value for Botox 8 U/kg vs placebo comparing MAS-B

p12: p value for Botox 4 U/kg vs placebo comparing MAS-B

p21: p value for Botox 8 U/kg vs placebo comparing CGI

p22: p value for Botox 4 U/kg vs placebo comparing CGI

$p1 = \max(p11, p21)$ ,  $p2 = \max(p12, p22)$ .

$p_1$  and  $p_2$  will be sorted in an increasing order to get  $p(1) \leq p(2)$ . The following decision rule will then be applied:

Step 1: If  $p(2) \leq 0.05$ , both doses are considered efficacious; otherwise go to step 2.

Step 2: If  $p(1) \leq 0.025$ , its corresponding dose is considered efficacious; otherwise go to step 3.

Step 3: Neither dose is considered efficacious.

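### The stated minimum power of 91% for the US FDA co-primary endpoints ignores the Hochberg rule; with 117 per group the floor for 8 U/kg is about 85%

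*Protocol*

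**What the plan says.** **Power statement.** Protocol Section 7.5 reads: "Using a 2-sample t-test, a significance level of 0.05, and the assumptions in Table 4, the power for MAS-B change from baseline is 94" percent. It bases the calculation on 8 U/kg and placebo only, gives 97% for CGI by Physician, and concludes that "the overall power for the US FDA co-primary endpoints will be at least 91" percent. The Protocol Summary repeats these figures, and Table 4 shows 91% in its overall row. The number analysed is given by "at least 351 patients (117 per treatment group) will complete the study". SAP Section 1.1 gives no power of its own and refers to Protocol Section 7.5.

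**Decision rule.** For the US FDA analysis, Protocol Section 7.7.1 says that "the maximum p value for the 2 co-primary endpoints in each dose will be used in the Hochberg procedure". SAP Section 10.1 repeats the rule. If the larger of the two dose-level p-values is at most 0.05, both doses succeed. If not, and the smaller is at most 0.025, "its corresponding dose is considered efficacious; otherwise go to step 3".

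**History.** Protocol Section 12.6 records that Amendment 3 replaced gatekeeping with Hochberg for the US FDA analysis. It lists no revision to Section 7.5.

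**The concern.** A fixed sequence that starts with 8 U/kg tests that dose at 0.05 whatever happens to 4 U/kg, and the 91% is correct for such a design. Hochberg makes the level for 8 U/kg depend on 4 U/kg. The level 0.05 is available only when 4 U/kg also has both p-values at or below 0.05. Otherwise 8 U/kg needs 0.025 on MAS-B and on CGI.

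The phrase "at least" claims a minimum. Section 7.5 assumes nothing about 4 U/kg, so the minimum has to cover the case in which 4 U/kg gives no help. The printed figure instead describes the most favourable testing level.

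At stake is the stated chance of success of the US registration analysis. Anyone relying on Section 7.5 would put the risk of failure for 8 U/kg at 9% when it may be about 15%. Type I error control and the analysis itself are not in question.

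**Working it through.** **Inputs**

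- MAS-B: means -0.8 and -0.45, difference 0.35, SD 0.75 (Protocol Table 4).
- CGI: means 1.2 and 0.6, difference 0.6, SD 1.2 (Protocol Table 4).
- n = 117 per group (Protocol Section 7.5), allocation 1:1:1 (Section 5.4), two-sided tests (Protocol Summary).
- Not in the documents, so varied as assumptions: the 4 U/kg effect and the correlation between endpoints.

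**Formula.** For a two-sample t-test, df = 2n - 2 = 232 and the noncentrality is (difference / SD) × √(n/2), with √(117/2) = 7.648.

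- MAS-B: (0.35/0.75) × 7.648 = 3.569
- CGI: (0.6/1.2) × 7.648 = 3.824

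Power is the probability that a noncentral t with these values exceeds the two-sided critical value, which is 1.970 at 0.05 and 2.256 at 0.025.

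**Step 1: reproduce the plan, then change only the level**

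| Two-sided level | MAS-B | CGI | Joint, product | Joint, lower bound |
|---|---|---|---|---|
| 0.05 | 94.5% | 96.8% | 91.4% | 91.2% |
| 0.025 | 90.5% | 94.1% | 85.1% | 84.6% |

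The product treats the endpoints as independent. The lower bound is the sum of the two powers minus 1 and holds for any correlation. The 0.05 row reproduces the printed 94%, 97% and 91% to within rounding. The 0.025 row is what 8 U/kg must meet when 4 U/kg fails.

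**Step 2: simulate the full rule.** 8 U/kg succeeds if its larger p-value is at most 0.025, or if both doses have larger p-values at most 0.05. There were 1,000,000 runs with a shared placebo arm, normal test statistics and the t critical values above. Power for 8 U/kg was:

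| 4 U/kg effect, as a share of 8 U/kg | Correlation 0 | 0.3 | 0.5 | 0.7 |
|---|---|---|---|---|
| None | 85.3% | 86.1% | 86.9% | 88.0% |
| Half | 85.7% | 86.6% | 87.3% | 88.4% |
| Three quarters | 87.9% | 88.5% | 89.2% | 90.1% |
| Equal | 90.5% | 90.9% | 91.3% | 92.0% |

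Only the last row comes to about 91%, so the printed figure is close to the best case.

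**Step 3: the n that would make 91% a floor.** The 0.025 product is 90.9% at 134 per group and 91.2% at 135. That is 3 × 135 = 405 completers. With 412 enrolled, it would require attrition of no more than 1 - 405/412 = 1.7%, whereas the plan implies 1 - 351/412 = 14.8%.

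**The case against.** **The planned analysis may be more powerful than the t-test.** The US FDA analysis is a covariate-adjusted MMRM on the mITT population. Patients who leave after week 6 still supply both endpoint visits, so more than 117 per group may contribute. With 127 per group the 0.025 product is 88.8%, and with all of about 137 randomized per group (412/3) it is 91.7%. Covariate adjustment could add more. This is a fair reason to expect actual power above 85%. But Section 7.5 states its power for a t-test on 117 per group, and the documents quantify no gain from the model. The like-for-like correction stays at about 85%.

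**"At least" may refer to the endpoints, not the doses.** The text does not say how 94% and 97% were combined, and 94 + 97 - 100 = 91 also fits as a bound valid for any correlation. That reading is plausible. The bound is still computed at 0.05, and at 0.025 it is 84.6%.

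**The trial can succeed on either dose.** The stated alternative is that at least one dose differs from placebo, and if the doses are equally effective the chance that at least one succeeds is about 96%. However, Section 7.5 ties its figure to 8 U/kg. On the either-dose reading, simulated power is still 85-88% if 4 U/kg has no effect and 86-89% at half effect, so 91% is not a minimum there either.

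**It is only a planning figure.** It does not enter the analysis, and every printed number is right at 0.05. This is true, and it limits the point to a mismatch between Sections 7.5 and 7.7.1 that wording can cure.

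**Conclusion.** The concern holds. Under the decision rule in Protocol Section 7.7.1 and SAP Section 10.1, the design does not guarantee 91% power for 8 U/kg on the US FDA co-primary endpoints. The floor is 85.1% with independent endpoints and 84.6% with no assumption about correlation, some 6 points below the printed figure. Over assumed correlations of 0 to 0.7, power for 8 U/kg runs from about 85-88% if 4 U/kg has no effect to about 90-92% if it is as effective as 8 U/kg.

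This rests on the Table 4 effects and SDs, a two-sample t-test and 117 per group, all taken from Section 7.5. The non-US analysis is unaffected, because gatekeeping tests 8 U/kg first at 0.05 and its 94% stands. A joint power of about 85% is still reasonable. The error is in stating 91% as a minimum.

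**What to change.** In the Protocol Summary (text and table), Section 7.5 and the overall row of Table 4:

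- Keep 94% and 97%, labelled as single-endpoint power at two-sided 0.05.
- Replace the overall US FDA figure with power for 8 U/kg under the Section 7.7.1 rule: about 85% if 4 U/kg does not succeed, rising to about 91% if it is as effective as 8 U/kg.
- State the 4 U/kg effect and the endpoint correlation assumed, and that the figures are for a t-test on 117 per group.

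If the sponsor wishes to rely on larger mITT numbers or on covariate adjustment, the numbers and correlations assumed should be given. SAP Section 1.1 can keep its reference to Section 7.5 once that section is corrected.

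The cost is a wording change and a less favourable stated figure. The sample size, the model and the testing procedure stay as they are.
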